4.1.2 Disposition of Participants and Withdrawals

Disposition will include tabulations for the number of participants screened and screen failed; the number and percentage of participants who: received treatment, completed study, reasons for study discontinuation/withdrawal (overall and by reason for study discontinuation/withdrawal); the number and percentage of participants in each analysis population will also be displayed. All the tabulations will be for SAF and by PH type and age group (0-<2, 2 - < 6, 6-<9, and 9 - 11 years).

4.1.3 Protocol Violations and Deviations

Prior to database lock, all protocol deviations will be reviewed, categorized as either ‘Important’ or ‘Non-important’, and finalized. Protocol deviations will be listed and summarized descriptively. All the tabulations will be for SAF and by PH type and age group (0-<2, 2 - < 6, 6-<9, and 9 - 11 years).

4.1.4 Demographics and Other Baseline Characteristics

Summary statistics for age, gender, race, ethnicity (where available, as ethnicity may not be collected at all sites), height/length, weight, and BSA will be presented for SAF and by PH type and age group (0-<2, 2 - < 6, 6-<9, and 9 - 11 years). Body mass index and body surface area will be computed as described in Section 4.1.1.6.

Summary statistics will be presented for baseline eGFR, time since PH diagnosis, number of kidney stone events in the last 12 months, and the number of kidney stones at baseline.

These summaries will be conducted for the MITT and SAF populations. All collected demographics and other baseline characteristics will be listed by participant.

The number and percentage of participants reporting various medical histories, grouped by Medical Dictionary for Regulatory Activities (MedDRA) system organ class (SOC) and preferred term (PT) (MedDRA; Version 26.0 or higher), will be tabulated for SAF and by PH type and age group.

Prior medications will be presented separately from concomitant medications. Medications that started prior to dosing on Day 1 will be considered prior medications whether they were stopped prior to Day 1 dosing or not. Missing dates will be handled using the methodology described in Section 4.1.1.7. Medications will be coded using World Health Organization drug dictionary (WHO-DD) version March 2023 or later. The number and percentage of participants reporting prior medication and concomitant medication use, grouped by ATC Level 2 and ATC Level 4, will be tabulated by PH type and age group. This analysis will be conducted for the SAF population. The prior medications and concomitant medications will be provided in a listing.

4.2 Primary Estimand Analyses

4.2.1 Definition of Endpoint

The primary endpoint is the percent change from baseline at Month 6 in spot urinary oxalate-to-creatinine ratio. The percent change from baseline at Month 6 in spot urinary oxalate-to-creatinine ratio will be calculated using formulas in section 4.1.1.6.

4.2.2 Main Analytical Approach

The primary analysis of the primary endpoint will be performed for MITT using a restricted maximum likelihood (REML) based MMRM approach with percent change from baseline at scheduled visits (Month 1 – Month 6) as the dependent variable. Analysis will include fixed effects of scheduled visits, baseline spot urinary oxalate-to-creatinine ratio, baseline age and baseline eGFR. Denominator degrees of freedom for the F-test for fixed effects will be estimated using the Kenward-Roger approximation. A compound symmetry (CS) covariance structure will be used to model the within-patient error given the small sample size for this study. The primary estimate is the least square (LS) mean of the percent change from baseline at Month 6. This LS mean will be presented along with corresponding standard errors (SEMs) and 95% confidence intervals (CI). Similar analysis will be performed to estimate the LS mean of the percent change from baseline averaged over Month 3 to Month 6.

Descriptive summary statistics (n, mean, standard deviation, median, minimum, maximum) for MITT population by PH type and by age group (0-<2, 2 - < 6, 6-<9, and 9 - 11 years) will also be provided.

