### 9.4.2. Primary Endpoint

The primary endpoint in this study is change from Baseline to Month 6 in spot urinary oxalate-to-creatinine ratio by PH1, PH2, or PH3 participant subgroups. The percent and absolute change in average spot urinary oxalate-to-creatinine ratio from Baseline to Day 180 will be summarized by PH1, PH2, or PH3 participant subgroups.

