No tables entries found.

Version History

This Statistical Analysis Plan (SAP) for study NN7022-PHYOX8 (Dicerna protocol number DCR-PHXC-203) is based on the protocol version V4.0, dated 23-Feb-2023.

SAP Version	Date	Change	Rationale
V2.0	12-Jan-2024	Update age groups for analysis from (0-5, 6-11) to (0 - <2, 2-< 6, 6-<9, 9-11)	Update age groups for analysis following FDA sNDA feedback.
V2.0	12-Jan-2024	Replace the categorical age groups with continuous age as covariate for MMRM modelling in Section 4.2.2	Considering that there are limited number of patients within each updated age group, continuous age variable may be used as a covariate in MMRM modelling.
V2.0	12-Jan-2024	Add sensitivity analysis on the ratio of spot urinary oxalate-to-creatinine ratio to the ULN in Section 4.2.3	Perform additional sensitivity analysis to adjust for the any potential confounding effect of natural maturity on spot urinary oxalate-to-creatinine ratio following FDA sNDA feedback.
V2.0	12-Jan-2024	Update MITT definition to include all PH types	Efficacy will be summarized by PH type.
V2.0	12-Jan-2024	The safety analysis of interim analysis will be based on Safety Analysis Set	All safety data will be included in the interim analysis following FDA sNDA feedback.

List of abbreviations

Abbreviation	Definition
AE	adverse event
AESI	adverse events special interest
ATC	anatomical therapeutic chemical
AUC	area under the curve
BLQ	below the limit of quantitation
BSA	body surface area
CRF	case report form
CS	clinically significant
CSR	clinical study report
ECG	electrocardiogram
eCRF	electronic case report form
EDC	electronic data capture
eGFR	estimated glomerular filtration rate
HR	heart rate
HRQOL	health related quality of life
IC or ICF	informed consent or informed consent form
ICH	International Council for Harmonization
LLOQ	lower limit of quantitation
MedDRA	Medical Dictionary for Regulatory Activities
MITT	modified intent-to-treat
N	number
PD	pharmacodynamic

Abbreviation	Definition
PE	physical examination
PH	primary hyperoxaluria
PK	pharmacokinetic
PKAP	pharmacokinetic analysis plan
PT	preferred term
QOL	quality of life
RR	respiratory rate
SAE	serious adverse event
SAP	statistical analysis plan
SAS®	a software system used for data analysis
SD	standard deviation
SOC	system organ class
TEAE	treatment-emergent adverse event
WHO	World Health Organization
WHO-DD	World Health Organization drug dictionary

1 Introduction

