1.1.2 Primary Estimand

The primary clinical question of interest is: What is the treatment effect of nedosiran in lowering urinary oxalate excretion (Uox) assessed via percent change from baseline in spot urinary oxalate-to-creatinine ratio at Month 6 in PH1 pediatric participants (birth to 11 years of age) with relatively intact renal function.

For the primary objective, the estimand is defined with five attributes:

- Treatment condition of interest is the monthly nedosiran administration.
- The target population is PH1 pediatric participants (birth to 11 years of age) with relatively intact renal function.
- The endpoint is percent change from baseline at Month 6 in spot urinary oxalate-to-creatinine ratio.
- The intercurrent events (ICEs) include treatment discontinuation for any reasons and will be handled by the treatment policy strategy.

[figure not shown]
Population-level summary is the percent change from baseline at Month 6 estimated by Mixed-effect Model Repeated Measures (MMRM) approach.

Rationale for estimand: The primary estimand assesses the treatment benefit of nedosiran in lowering urinary oxalate-to-creatinine ratio that can be expected in clinical practice, provided that the treatment adherence in the study reflects what would be seen in clinical practice.

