2.1 Multiplicity Adjustment

Not applicable.

3 Analysis Sets

The following analysis populations are planned for this study:

Participant Analysis Set	Description
Safety Population (SAF)	
The safety population includes all participants who received at least 1 dose of study intervention.
Modified Intent-To-Treat Population (MITT)	
The MITT population includes all participants who received at least 1 dose of study intervention and have at least 1 post-baseline spot urinary oxalate to creatinine ratio. The MITT population is for efficacy analysis.
Evaluable Population (EVAL)	
The evaluable population includes all participants in the MITT population who received 6 full doses of study intervention and completed through the Day 180 Study Visit.
Pharmacokinetic Population (PK)	
The PK population will be defined in PK analysis plan (PKAP).
Per-Protocol Population (PP)	
The PP population includes all PH1 participants who received at least 1 dose of study intervention and had no major protocol deviations that affect efficacy endpoint assessment as adjudicated by the sponsor.
Interim Analysis Population	
The Interim Analysis population includes first 15 PH1 participants who completed the study.

4 Statistical Analyses

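### The primary estimand is for PH1 only, but the primary MMRM pools all PH types in MITT with no PH-type term, so its LS mean is for a different population

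*SAP*

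**What the plan says.** **Estimand (SAP 1.1.2).** "The target population is PH1 pediatric participants (birth to 11 years of age) with relatively intact renal function". The fifth attribute ties the estimand to the model: "Population-level summary is the percent change from baseline at Month 6 estimated by Mixed-effect Model Repeated Measures (MMRM) approach".

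**Estimator (SAP 4.2.2, under the Section 4.2 heading for the primary estimand analyses).** "The primary analysis of the primary endpoint will be performed for MITT using a restricted maximum likelihood (REML) based MMRM approach". On the model terms: "Analysis will include fixed effects of scheduled visits, baseline spot urinary oxalate-to-creatinine ratio, baseline age and baseline eGFR". One LS mean at Month 6, with its standard error and 95% CI, is named as the primary estimate. For this endpoint, output by PH type is limited to descriptive statistics.

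**Analysis sets (SAP Section 3).** "The MITT population includes all participants who received at least 1 dose of study intervention", provided they also have a post-baseline ratio; PH type is not mentioned. EVAL is a subset of MITT. PP is limited to PH1 participants without major deviations that affect efficacy assessment. The interim set is the first 15 PH1 completers.

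**Version history (SAP V2.0).** The change reads "Update MITT definition to include all PH types", and the reason given is "Efficacy will be summarized by PH type".

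**Protocol 9.4.2.** Percent and absolute change in the average ratio "will be summarized by PH1, PH2, or PH3 participant subgroups". Protocol Section 3 words the primary endpoint by PH type as well.

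**The concern.** The question is asked about one disease type and answered in a set that may hold three. If PH2 and PH3 respond like PH1, little is lost. The protocol gives reason to doubt that. In its account of the randomised six-month study (Section 2.2.3.1), PH1 showed a significant reduction against placebo, while individual PH2 data showed no consistent fall. Section 2.1 calls the PH2 efficacy results inconclusive. The PH3 study missed its efficacy endpoint.

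Two things are at stake. First, the number reported as the primary estimate would carry a PH1 label from the estimand but would shift with the enrolment mix. Second, SAP 4.2.3 repeats the MMRM in EVAL (all types) and PP (PH1 only). If PP differs from MITT or EVAL, the reader cannot tell whether PH type or protocol deviations explain it.

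**Working it through.** The plan has no sample-size, power or precision figure to reproduce. The check therefore has a textual part and an illustration of size.

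**Text, side by side**

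| Item | PH types covered |
|---|---|
| Estimand target population (SAP 1.1.2) | PH1 |
| Primary MMRM on MITT (SAP 4.2.2) | all, no type term |
| EVAL sensitivity MMRM (SAP 4.2.3) | all, no type term |
| PP sensitivity MMRM (SAP 4.2.3) | PH1, no major deviations |
| Interim efficacy set (SAP Section 3 and 4.7) | PH1, first 15 completers |
| Descriptive tables (SAP 4.2.2) | each type separately |

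No row is a model estimate for all PH1 participants in MITT, which is what the estimand asks for.

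**Inputs for size**

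- Enrolment: Protocol 1.1 gives about 25 enrolled, about 20 completing, and a goal of about 15 PH1. Taking 15 PH1 among 20 is an inference.
- PH1 change: -40% to -64%, assumed. The -64% is the mean maximum fall in 24-hour urinary oxalate in the single-dose study, which mixed PH1 and PH2 (Protocol 2.2.3.1). The -40% has no source in the documents.
- Non-PH1 change: 0% to -24.5%, assumed. The -24.5% is the PH3 mean at Day 85 after one dose in 4 participants, again in 24-hour oxalate. The 0% stands for no response.

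**Formula.** With w the PH1 share, pooled mean = w × m(PH1) + (1 - w) × m(other). The gap from the PH1 mean is (1 - w) × [m(other) - m(PH1)].

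| Non-PH1 | Smallest gap (PH1 -40, other -24.5) | Largest gap (PH1 -64, other 0) |
|---|---|---|
| 0 of 15 | 0 | 0 |
| 1 of 16 | 0.0625 × 15.5 = 1.0 | 0.0625 × 64 = 4.0 |
| 5 of 20 | 0.25 × 15.5 = 3.9 | 0.25 × 64 = 16.0 |

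Units are percentage points of change from baseline. Every non-zero gap is toward a smaller reduction.

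**Check that the covariates do not remove the gap.** A simulation fitted the 4.2.2 model by REML, with a random intercept for compound symmetry and fixed effects for visit, baseline ratio, age and eGFR. It used 100 replicates, with between- and within-patient SDs of 15 points assumed and covariates generated independently of PH type. Some fits gave convergence warnings, so the decimals are approximate. The true PH1 change was set at -50%, with 15 PH1 and 5 others.

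| Change in others | Identity | Pooled MMRM (SE) | PH1-only MMRM (SE) |
|---|---|---|---|
| 0% | 0.75 × (-50) + 0.25 × 0 = -37.5 | -38.1 (6.8) | -50.6 (5.4) |
| -24.5% | 0.75 × (-50) + 0.25 × (-24.5) = -43.6 | -43.5 (5.3) | -49.9 (5.4) |

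The pooled LS mean follows the mixture, as expected. Its SE is larger than the PH1-only SE in one scenario and about equal, marginally smaller, in the other.

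**The case against.** The best case for the plan is that a PH1 answer will exist and that nothing formal depends on the primary number. MITT percent change is already to be described by PH type, which delivers the summary that Protocol 9.4.2 asks for. The PP model is PH1 only, and so is the interim efficacy set, whose 15 participants equal the planned PH1 goal. No hypothesis is tested. Under the assumptions above, pooling makes the drug look less effective in PH1, so it does not inflate a claim. PH2 is described as much rarer than PH1 (Protocol 2.2.1) and PH3 enrolment is conditional (Protocol 4.1), so few non-PH1 participants may enrol.

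Most of this stands as a limit on size. It does not close the gap. The descriptive tables give no LS mean, standard error or CI. PP drops PH1 participants with major deviations, and the interim set holds completers only; both fit poorly with a treatment-policy estimand. A descriptive trial still needs its headline estimate to describe the population it names.

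A reader might go further and infer any of the following, which the documents do not support:

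- *Pooling must widen the CI.* The simulation shows it can go either way.
- *The sensitivity analyses cannot be interpreted.* Only comparisons against PP confound type with adherence. EVAL is drawn from MITT with no type rule, and the LLOQ run repeats the same analyses.
- *The protocol requires PH2 and PH3 to be reported participant by participant.* It asks for subgroup summaries.
- *The sponsor chose to answer a different question.* The V2.0 rationale speaks of summaries by type, which points to an edit not carried through to 4.2.2.

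**Conclusion.** The mismatch is certain from the text: a PH1 estimand, an all-type analysis set, and a model that neither restricts to PH1 nor separates the types. Followed as written, with any non-PH1 participant in MITT, the primary LS mean does not target the stated estimand. Nor does it supply a result by type.

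The size is conditional. It is zero with no non-PH1 participants, about 1 to 4 points with one among 16, and about 4 to 16 points with five among 20. In the last two cases the PH1 reduction is understated. These figures rest on assumed effects borrowed in part from 24-hour oxalate in other studies and other dosing, and on an enrolment mix that the plan does not fix. Setting 15 PH1 against 25 enrolled would suggest a larger gap, but the protocol nowhere plans for ten non-PH1 participants, and its Sections 4.1 and 9.2 describe the 25 as screened.

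**What to change.** In SAP 4.2.2, state that the primary MMRM is run in PH1 participants of the MITT population, and apply the same restriction to the Month 3 to Month 6 average. In SAP 4.2.3, restrict the MITT and EVAL model runs to PH1 in the same way: percent change, the LLOQ run, absolute change, and the ratio to ULN. MITT, EVAL and PP would then all be PH1 sets and would not differ by PH type. Keep the planned descriptive summaries by PH type for PH2 and PH3, and leave the MITT definition as it is.

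Two alternatives are weaker. A PH-type term would serve only if the PH1 LS mean were the named estimate, and few PH2 or PH3 participants would support it. Widening the estimand to all types would remove the contradiction with 1.1.2, but a single pooled mean would still not give the protocol's by-type result.

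The cost is a wording change and one subset condition, with no new data. The primary model would rest on about 15 participants instead of about 20, which is what a PH1 estimand implies. The change alters what the primary number estimates, so it should be settled before database lock.

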#### **Key exclusion criteria include**

- Renal or hepatic transplantation (prior or planned within the study period)
- Plasma oxalate (Pox)  $> 30 \text{ } \mu\text{mol/L}$  at Screening
- Documented evidence of clinical manifestations of severe systemic oxalosis (including preexisting retinal, heart, or skin calcifications, or history of severe bone pain, pathological fractures, or bone deformations)

**Number of Participants:** Approximately 25 participants will be enrolled such that approximately 20 participants (approximately 7 aged 6 to 11 years; approximately 10 aged 1 to

[figure not shown]
5 years; and approximately 3 aged < 1 year) complete the study, with an overall goal of approximately 15 PH1.

**Intervention Groups and Duration of Participation:** This study has a single intervention group in which all participants will receive monthly SC doses of nedosiran over a 6-month period. Prospective participants will be screened over an up-to-35-day period, with an extra 14 days allowed for participants who are required to repeat initially unanalyzable screening laboratory assessment samples. The total time on study for each participant is approximately 7 months.

**Study Duration:** Approximately 24 months from the first participant, first visit, to the last participant, last visit.

**Safety Review Committee:** This study will utilize an SRC to review safety and efficacy data on a periodic basis.

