- p Physical examination includes height/length, weight, inspection of injection site(s), and review of body systems. A full physical exam will be performed at Screening and Day 180 (or early termination). For at-home visits, the home-health nurse will provide in-person support to the Investigator in assessing the participant; height and weight will not be measured during at-home visits. The physical examination performed at other scheduled visits (Days 1 through Day 150) or unscheduled visits may be a brief or full physical examination at the Investigator's discretion. See Section 8.2.1 and Section 8.2.2.
- q The total dose will be based upon body weight recorded on study Day 1. For participants < 6 months of age at Screening, the dose will be adjusted at Day 90 to capture changes in weight; no other dose adjustments are allowed.
- r Blood samples for hematology and serum chemistry to be collected predose on dosing days. A single blood draw to be performed at other visits, as indicated. See Section 10.2 for the list of parameters.
- s Blood samples for coagulation studies to be collected predose. Coagulation panel will include prothrombin time (PT) and international normalized ratio (INR). Additional coagulation studies may be performed as clinically indicated.
- t Estimated glomerular filtration rate (eGFR) to be calculated only in participants aged 12 months and older, as described in Section 8.2.6.1.
- u Urinalysis with microscopy at Screening and as clinically indicated. Dipstick urinalysis may be performed at other scheduled visits. Collect sample for urinalysis before dosing. See Section 10.2 for parameters.
- v A positive urine pregnancy test will be confirmed with a serum pregnancy test. Administration of study intervention will be discontinued in any participant with a positive pregnancy test. A final pregnancy test will be conducted 2-3 weeks following the last dose of study intervention in any WOCBP who prematurely discontinues the study.
- w Parent(s)/legal guardian will report instances of renal stones requiring medical intervention, stone passage, and/or renal colic requiring medication (Section 8.1.3.1).
- x In the event of rescreening, if a participant had been screened for this study within the last 3 months and had ultrasound data sent to the central over-readers, repeat of the ultrasound will not be required during the rescreen.

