### 8.2.6.1. Estimated Glomerular Filtration Rate (eGFR)

The eGFR (mL/min/1.73 m^2) will be calculated using the multivariate Schwartz equation in participants aged 12 months and older (Figure 2).

In Japan, eGFR (mL/min/1.73 m^2) will be calculated using the Uemura creatinine-based equation in participants aged 2 years and older (Figure 3) or the Uemura cystatin C-based equation in participants aged 12 months to < 2 years (Figure 4).

Estimating GFR in infants is challenging because GFR measured using exogenous markers is burdensome and is not routinely performed in this population. As participants enrolled as infants younger than 12 months of age will not have a baseline eGFR recorded, no calculation of eGFR will be required as these participants age up throughout the study. In these participants younger than 12 months of age, serum creatinine will be monitored for renal health (see Section 8.2.6).

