4.1.1.3 Handling of Dropouts or Missing Data

4.1.1.3.1 Missing Efficacy Endpoint Data

While all possible efforts will be made to ensure that participants stay in the study and all data is collected as scheduled, the occurrence of missing data cannot be eliminated.

Participants who sign the informed consent form but do not receive the study intervention may be replaced. Should there be a participant(s) who signs the informed consent form, and receives the study intervention and subsequently withdraws, or is withdrawn or discontinued from the study before the Day 180 Visit, an additional participant(s) in the same age group may be enrolled to ensure that an adequate number of participants complete the Day 180 visit assessments.

No other imputation will be used in the study except for partial dates described in Section [4.1.1.7](#).

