4.1.1.6 Derived Variables

- Change from baseline = value at current time point – baseline value
- Percentage change from baseline = $\left(\frac{\text{value at current time point} - \text{baseline value}}{\text{baseline value}} \right) * 100\%$
- Spot urinary oxalate-to-creatinine ratio = the average of all the spot urinary oxalate-to-creatinine ratio collected at the specific visit.
- Treatment-emergent AE (TEAE) = any AE with an onset date/time on or after administration (including any partial administration) of the first dose of study intervention and until the study completion date from the end of study CRF.
- Body surface area will be calculated using the following formula (DuBois & DuBois, 1916):
$$BSA = (\text{Weight}^{0.425} \times \text{Height}^{0.725}) \times 0.007184;$$
 with weight in kilograms and height in centimeters.
- Body mass index (BMI) will be calculated using the formula: $\text{Weight [kg]} / (\text{Height}^2 [\text{m}^2])$.
- Estimated Glomerular Filtration Rate (eGFR) will be calculated as described in Protocol Section 8.2.6.1.
- Annualized stone event rate will be derived as number of stone events in the exposure period / total number of years exposed.

The number of stone events will be calculated as the number of discrete (non-concurrent) adverse events marked as a Kidney Stone Event on the adverse event CRF. Kidney stone events include renal stone requiring medical intervention, stone passage with or without hematuria, and renal colic requiring medication.

Concurrent events will be defined as events occurring within the same 4-week (28-day) window. For example, renal colic treated with medication on Monday 12 November 2019 followed by stone passage without hematuria on Friday 30 November 2019 is a single (concurrent) stone event (18 days between start and stop of single stone event). Renal colic treated with medication on Monday 12 November 2019 followed by stone passage without hematuria on Wednesday 13 December 2019 is considered two separate stone events (30 days between discrete event one and event two).

- Quality-of-life Questionnaires:

PedsQL

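### The primary MMRM adjusts for baseline eGFR, which participants enrolled under 12 months do not have by design, so its estimates omit them although the estimand runs from birth to 11 years

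*SAP*

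**What the plan says.** SAP 4.2.2 fits a REML-based MMRM to percent change at Months 1 to 6 in MITT: "Analysis will include fixed effects of scheduled visits, baseline spot urinary oxalate-to-creatinine ratio, baseline age and baseline eGFR". The primary estimate is the Month 6 LS mean with its 95% CI.

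For eGFR itself, SAP 4.1.1.6 adds no equation of its own; it "will be calculated as described in Protocol Section 8.2.6.1". That protocol section starts at 12 months, as do its two equations for Japan, and it gives the consequence: "As participants enrolled as infants younger than 12 months of age will not have a baseline eGFR recorded", no calculation is needed later as they grow older. The eGFR footnote to the Schedule of Activities agrees ("to be calculated only in participants aged 12 months and older").

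On missing data, SAP 4.1.1.3.1 says "No other imputation will be used in the study except for partial dates described in Section" 4.1.1.7. Neither document says what to do when a covariate is missing.

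On who should be described, SAP 1.1.2 states: "The target population is PH1 pediatric participants (birth to 11 years of age) with relatively intact renal function". MITT (SAP Section 3) needs one dose and that participants "have at least 1 post-baseline spot urinary oxalate to creatinine ratio"; it does not require an eGFR. The protocol synopsis plans for infants: "Approximately 25 participants will be enrolled such that approximately 20 participants (approximately 7 aged 6 to 11 years; approximately 10 aged 1 to" 5 years, and about 3 under 1 year), with a goal of about 15 PH1.

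**The concern.** The model needs a value that one planned age stratum cannot supply. The estimand and the analysis set admit infants, the protocol qualifies them on serum creatinine because eGFR is not available, and the model then leaves them out without the SAP saying so. The SAP does restrict the secondary eGFR endpoint to participants aged at least 12 months (4.3.1.1), but it does not carry that limit over to the model that uses the same variable as a covariate.

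What is at stake is whom the headline estimate describes. Because the study tests no hypothesis, the LS mean and its interval are the main model-based efficacy output. The loss is also systematic by age. SAP 4.2.3 adds an analysis of the ratio relative to an age-specific ULN, to deal with natural maturation. If it uses the same covariates, it loses the children whose reference limit changes fastest.

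**Working it through.** **The plan's own count.** The age strata in the synopsis give 7 + 10 + 3 = 20 completers, matching the stated total. There is no alpha, power, effect size or SD to reproduce, because no formal sample size calculation was done.

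**Who enters the model.** A likelihood-based mixed model tolerates missing outcomes, but it drops a record whose covariate is missing. Baseline eGFR is constant within a participant, so an infant loses all six visits.

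- With the eGFR term: 20 − 3 = 17 participants and 17 × 6 = 102 visit records.
- Without it: 20 participants and 20 × 6 = 120 records.
- Loss: 3/20 = 15% of completers, and the whole under-1 stratum.

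**PH1 only.** SAP 4.2.2 names MITT, which includes all PH types, while the estimand is PH1. The documents do not say how many infants have PH1. With 0 to 3 of about 15, the loss is 0/15 = 0% to 3/15 = 20%, leaving 15 to 12 participants.

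**Shift in the mean.** If the mean percent change is m in older children and m + D in infants, the mean over all 20 is (17m + 3(m + D))/20 = m + 0.15D. D is not in the documents; I assume 10 to 40 points.

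- 20 completers: 0.15 × 10 = 1.5 to 0.15 × 40 = 6 points.
- 15 PH1 participants, if all 3 infants have PH1: 0.20 × 10 = 2 to 0.20 × 40 = 8 points.

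This treats the LS mean as a simple mean, so it indicates size only.

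**Precision.** If residual variance is unchanged, the SE ratio for 17 against 20 is √(20/17) = 1.085, a rise of roughly 8%. For 12 against 15 it is √(15/12) = 1.118.

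**Maturation.** The SAP does not tabulate the ULN, so I take half the inclusion cut-offs in Protocol 5.1 as the age reference:

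| Age boundary | Reference (mol/mol) | Fall |
|---|---|---|
| 6 months | 0.22 to 0.17 | 23% |
| 12 months | 0.17 to 0.13 | 24% |
| 2 years | 0.13 to 0.10 | 23% |
| 3 years | 0.10 to 0.08 | 20% |

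The percentage steps in infancy are no larger than at 2 years. What differs is the spacing. The first two boundaries are six months apart and treatment lasts six months, so practically every infant crosses one during the study.

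**The case against.** Several points on the other side stand.

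- **Infants are not lost from the primary endpoint.** A reader might infer that they drop out of the efficacy evaluation. They do not. SAP 4.2.2 also requires descriptive summaries of MITT by PH type and by age group, including 0 to <2 years. Protocol 9.4.2 defines the primary analysis as a summary by PH type, and the responder endpoint in SAP 4.3.1.1 keeps infants too.
- **No decision depends on the model.** There is no confirmatory test and no success threshold (SAP Section 2; Protocol 9.1 and 9.4.1), so no pass or fail result can change.
- **The SAP does not expressly forbid imputing eGFR.** The sentence in 4.1.1.3.1 stands under missing efficacy endpoint data, and the SAP fills in values below the quantification limit elsewhere. It is better read as silent on missing covariates. That silence does not help, because those other rules cannot create an eGFR that was never calculated.
- **The number of infants is only a target**, and the difference D is assumed.
- **Removing eGFR is not free.** Eligibility runs from 30 mL/min/1.73 m² upward, so eGFR may be prognostic and improve precision even in a single-arm study. Including infants also brings in their natural fall in the raw ratio, in the favourable direction and with no control arm. If an infant's ratio fell in line with the reference limit (assumption), three of 20 would contribute 0.15 × 23% to 0.15 × 24%, about 3.5 points. A linear term for baseline age does not remove this, because the LS mean is still averaged over the infants.

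One might also infer that the reported MITT count would misstate the number analysed. The table shells are not among these documents, so that cannot be judged.

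**Conclusion.** Wrong as written, and it should be fixed. The stated model, followed literally, estimates the effect in participants enrolled at 12 months or older, while the estimand and MITT run from birth. This holds for the primary LS mean, its Month 3 to 6 average, and every analysis in SAP 4.2.3 that reuses the model: the EVAL and PP repeats, the quantification-limit repeat, absolute change and, if its covariates are unchanged, the ULN ratio.

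On planned numbers 17 of 20 completers contribute. For PH1 the loss is anywhere from none to 3 of about 15. If no infants enrol, there is no effect. The 1.5 to 6 point shift rests entirely on the assumed 10 to 40 point difference, and the 8% rise in SE on unchanged residual variance.

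The documents do not support a stronger conclusion, such as that the trial's efficacy assessment fails or that infants go unreported. The fault is a mismatch between a declared population and a model-based estimate in a descriptive study.

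**What to change.** - In SAP 4.2.2, and wherever 4.2.3 repeats the model, remove baseline eGFR and keep visit, baseline ratio and baseline age.
- Fit the eGFR-adjusted model as a labelled sensitivity analysis in participants aged 12 months or older.
- Report the number of participants contributing to each model beside its estimate.
- Read the ULN-ratio analysis, now with infants in it, alongside the primary estimate, because the raw ratio will carry their age-related fall.

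The cost is one model term and a few lines of SAP text, plus possibly some precision if eGFR is prognostic.

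Two alternatives would also restore consistency: a renal covariate defined at every age, such as serum creatinine relative to its age reference, or an estimand openly limited to 12 months and older with infants reported descriptively. A missing-eGFR indicator is less attractive: it would in effect be an under-12-months indicator resting on about 3 participants.
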